## 5.6 Benefit/risk assessment

There is an unmet medical need for new therapies for use in subjects with moderate-to-severe AD as current immunosuppressive medications, such as cyclosporine, methotrexate, and azathioprine, have associated long-term toxicities.

Tralokinumab has already demonstrated efficacy in moderate-to-severe AD, and has shown an acceptable safety profile in AD, asthma, ulcerative colitis, idiopathic pulmonary fibrosis, and in trials with healthy subjects. The evidence discussed in Section 5.2 further supports the hypothesis that tralokinumab may benefit individuals with AD.

In clinical trials completed to date tralokinumab was well tolerated. A number of theoretical potential risks have been identified that are described in the current version of the Investigator's Brochure, including hypersensitivity reactions, immune complex disease, severe infections, malignancies, and interference with reproductive function; measures are in place in this trial to protect participating subjects as follows:

- Close monitoring of subjects during the trial with trial visits every 2 weeks during the treatment period (see the schedule of trial procedures in Section 4).
- Close monitoring of subjects during the post-dosing period (at the first 3 IMP dosing visits) as a precautionary measure against hypersensitivity reactions (further details are given in Section 9.2).
- Monitoring of subjects for clinical manifestations that may be associated with the development of specific antibodies to tralokinumab (i.e., immune complex disease).
- Exclusion of subjects with untreated systemic helminth infestations or subjects who have failed to respond to standard of care therapy. Neutralisation of IL-13 might theoretically cause a worsening of parasitic infestation, in particular, prevention of expulsion of gastrointestinal worms (helminths) (20).
- Exclusion of subjects with a history of tuberculosis requiring treatment within 12 months prior to the screening visit.

- Exclusion of subjects with a history of a clinically significant infection (defined as a systemic or serious skin infection requiring parenteral antibiotics, antiviral, or anti-fungal medication; see Section 8.3) within 4 weeks prior to baseline which, in the opinion of the investigator or sponsor's medical expert, may compromise the safety of the subject in the trial.

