### 10.2 IMP discontinuation rules

#### 10.2.1 Reasons for permanent discontinuation of IMP

Subjects will be permanently discontinued from IMP in the event of:

- Anaphylactic reaction or other severe systemic reaction to IMP injection.
- An AE that, in the opinion of the investigator or sponsor's medical expert, contraindicates further dosing.
- Diagnosis of a malignancy during the trial, excluding carcinoma in situ of the cervix, or localised squamous or basal cell carcinoma of the skin.
- Evidence of pregnancy.
- Any infection that is opportunistic, such as active tuberculosis and other infections whose nature or course may suggest an immuno-compromised status.
- Severe laboratory abnormalities:
  - ALT and/or AST values >3x ULN with total bilirubin >2x ULN (unless elevated bilirubin is related to Gilbert-Meulengracht Syndrome).
  - Confirmed AST and/or ALT >5x ULN (for more than 2 weeks).

Refer to Section [10.3](#) for details on the handling of subject discontinuation and to [Panel 2](#) for assessments to be performed at an early termination visit for subjects who discontinue IMP permanently.

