**Panel 12: Adverse events of special interest**

Adverse event of special interest	Additional information to be provided
Eczema herpeticum	Skin findings: 
 
• Lesion type (papules, vesicles, crusts, eroded pits, other).
 
• Disseminated / localised.
 
• Location (face, scalp, back, chest, upper limb, lower limb, genitals).
 
• Present in an area with visible eczema / no visible eczema / present in areas with and without eczema.
 
• Monomorphic / polymorphic.
 
 Confirmation of herpes simplex virus (not confirmed, PCR, viral culture, Tzanck, other)
Malignancies diagnosed after randomisation, excluding basal cell carcinoma, localised squamous cell carcinoma of the skin, and carcinoma in situ of the cervix	
 
• Histology report available
 
• Oncology assessment available
 
• Treatments (surgery, radiation, chemotherapy, other)
 

Skin infections requiring systemic treatment	
 
• Location (face, scalp, back, chest, upper limb, lower limb, genitals)
 
• Outcome of pathogenic skin swab (positive, negative, not performed)
 

Conjunctivitis	
 
• Aetiology (viral, bacterial, allergic, unknown)
 
• Bacterial culture outcome (for events with bacterial aetiology)
 
• Diagnosis confirmed by ophthalmologist
 

Keratoconjunctivitis	
 
• Aetiology (infectious, non-infectious, other, unknown)
 
• Bacterial culture outcome (for events with bacterial aetiology)
 
• Diagnosis confirmed by ophthalmologist
 

Keratitis	
 
• Aetiology (infectious, non-infectious, other, unknown)
 
• Bacterial culture outcome (for events with bacterial aetiology)
 
• Diagnosis of herpes simplex keratitis (for events with viral aetiology)
 
• Diagnosis confirmed by ophthalmologist
 

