#### **14.3.8.1 Adverse events**

AEs will be coded during the course of the trial according to Medical Dictionary for Regulatory Activities (MedDRA). AEs will be presented by preferred terms and primary system organ class (SOC).

Treatment-emergent AEs will be summarised, however, all AEs recorded during the course of the trial will be included in the subject data listings. An event will be considered treatment-emergent if started after the first use of IMP or if started before the first use of IMP (applicable if subject had a wash-out) and worsened in severity thereafter. The tabulations described in the following will only include the treatment-emergent events. In each of the tabulations, AEs will be defined by MedDRA preferred terms within primary SOC.

An overall summary of the number of treatment-emergent AEs, number (percentage) of subjects with any treatment-emergent AEs, SAEs, deaths, premature discontinuations from the trial due to AEs, treatment-related AEs and severe AEs will be presented.

The number of AEs and the number of subjects experiencing each type of AE will be tabulated by treatment group. The percentage of subjects with AEs will be compared between treatment groups by a chi-square test or Fisher's exact test (if expected cell count < 5).

The severity for each type of AE will be tabulated by treatment group.

The causal relationship to IMP (tralokinumab/placebo) for each type of AE will be tabulated by treatment group. Related AEs are defined as AEs for which the investigator has not described the causal relationship to IMP as 'not related'. The number of related AEs and the number of subjects experiencing each type of related AE will be tabulated. The percentage of subjects with related AEs will be compared between treatment groups by a chi-square test or Fisher's exact test (if expected cell count <5).

The causal relationship to IMP (each vaccine) for each type of AE will be tabulated by treatment group. Related AEs are defined as AEs for which the investigator has not described the causal relationship to IMP as 'not related'. The number of related AEs and the number of subjects experiencing each type of related AE will be tabulated. The percentage of subjects with related AEs will be compared between treatment groups by a chi-square test or Fisher's exact test (if expected cell count <5).

SAEs and AESIs will be evaluated separately and a narrative for each will be given. AEs leading to withdrawal from trial will be listed.

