6.8 Analysis of safety

6.8.1 Adverse events

AEs will be summarised and listed.

Assignment of AEs to periods

An AE will be assigned to a given period (treatment period or safety follow-up) if the start date is after the start date and before the end date of that period (see Section 6.9.2, Table 6).

For AEs with start day on the same day as the first dose was given, only AEs starting after the first dose was given will be considered treatment-emergent and assigned to the treatment period.

AEs starting on the day of exposure end (as defined in Section 6.9.2) will be assigned to the safety follow-up treatment period.

For handling of incomplete start dates of AEs, see Section 6.9.3.

Sort order of AE tables

Generally, AE tables by system organ class and/or preferred term will be sorted by decreasing number of affected subjects in the Tralokinumab group.

Other adverse events

A MedDRA search on all reported AEs was specified to capture AEs belonging to injection site reactions. The MedDRA search to capture this safety area of interest was performed using the following HLT levels (based on primary and secondary terms): ‘administration site reactions NEC’, ‘application and instillation site reactions’, and ‘injection site reactions.

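### Adverse events are compared by arm term by term, but hypersensitivity and immune complex disease have no pre-specified grouped count, and severe infections only a partial one

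*SAP*

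**What the plan says.** Protocol 5.6 (Benefit/risk assessment) refers to theoretical potential risks described in the Investigator's Brochure, "including hypersensitivity reactions, immune complex disease, severe infections, malignancies, and interference with reproductive function". It then lists protective measures, among them observation after the first three dosing visits as a precaution against hypersensitivity, and monitoring for signs of immune complex disease.

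Protocol 14.3.8.1 sets the level of the AE analysis: "In each of the tabulations, AEs will be defined by MedDRA preferred terms within primary SOC". At that level the arms are set side by side: "The number of AEs and the number of subjects experiencing each type of AE will be tabulated by treatment group", and "The percentage of subjects with AEs will be compared between treatment groups by a chi-square test" or Fisher's exact test when expected counts are small. Severity and causality are also tabulated by arm. SAEs and AESIs are evaluated separately, with narratives.

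Panel 12 defines six AESI categories: eczema herpeticum, malignancies, skin infections ("Skin infections requiring systemic treatment"), conjunctivitis, keratoconjunctivitis and keratitis.

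SAP 6.8.1, under Other adverse events, adds one dictionary search: "A MedDRA search on all reported AEs was specified to capture AEs belonging to injection site reactions". It uses three high-level terms and looks at both primary and secondary terms.

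**The concern.** The protocol identifies particular risks and sets up monitoring for them, but the analysis plan does not carry all of them through to a summary. Of the five risks, malignancies have an AESI category and infection has two partial ones. Hypersensitivity and immune complex disease have neither an AESI category nor a search. The one search that is planned concerns a topic outside the five.

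Safety and tolerability with concomitant vaccines is an additional secondary objective (Protocol, Panel 3), and the Week 16 analysis is meant to support a marketing submission (Protocol 9.3.1). A reader of the report will ask how many subjects in each arm had a hypersensitivity-type event. The planned tables do not answer that. Adding their lines may count one subject several times, and choosing which lines to add after unblinding would be data-driven.

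**Working it through.** The plan states no figure on this point, so there is none to reproduce. The check is a comparison of the texts, followed by an illustration with assumed rates.

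**1. Each named risk against the planned summaries**

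| Risk in Protocol 5.6 | AESI category (Panel 12) | Search (SAP 6.8.1) | By-arm subject count for the risk as a group |
|---|---|---|---|
| Hypersensitivity, including anaphylaxis | none | none | none specified |
| Immune complex disease | none | none | none specified |
| Severe infections | eczema herpeticum; skin infections needing systemic treatment | none | partial |
| Malignancies | yes, with listed exclusions | none | AESI group |

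The fifth risk, interference with reproductive function, is not pursued here.

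**2. Can a planned line stand in for the group?** Only if nearly all events of a risk receive one preferred term or make up one SOC. The documents do not reproduce the MedDRA hierarchy, so the degree of scatter is an assumption. They do give a reason to expect some: the anaphylaxis criteria in Protocol Appendix 5 combine skin or mucosal, respiratory, blood-pressure and gastrointestinal signs. The comparison of percentages in 14.3.8.1 does not help. Read as any AE it compares the overall total, and read as each type of AE it compares single lines.

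**3. What scatter can cost**

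Inputs: 200 subjects randomised 1:1 (Protocol 14.1), so about n = 100 per arm in the safety analysis set. Event rates are assumed, because the documents give none. The test is two-sided Fisher at 5%.

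Power = sum of Bin(x; 100, pT) × Bin(y; 100, pC) over all (x, y) with Fisher p ≤ 0.05.

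With an even split over five terms, each line has rates pT/5 and pC/5. Power for at least one of five lines, treated as independent, is 1 − (1 − q)^5, where q is the power per line.

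| Assumed rates | One grouped count | Per line, five equal terms | Any of the five lines |
|---|---|---|---|
| 10% v 2% | 58.7% | 1.1% (2% v 0.4%) | 1 − (1 − 0.0106)^5 = 5.2% |
| 12% v 3% | 61.2% | 1.9% (2.4% v 0.6%) | 9.4% |
| 10% v 1% | 76.9% | 1.3% (2% v 0.2%) | 6.3% |

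In observed counts, 10 v 2 subjects gives p = 0.033, while a single line of 2 v 0 gives p = 0.50.

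**4. Where the loss is smaller**

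- Even split of 10% v 2% over three terms: 6.7% per line.
- 70% of the same excess on one line (0.7 × 10% = 7% v 0.7 × 2% = 1.4%): 36% for that line.
- A very rare risk, 3% v 0.5% even when grouped: about 5%. An observed 5 v 0 gives p = 0.059, and 6 v 0 is the first split against zero below 0.05 (p = 0.029).

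**The case against.** A reader might infer that these risks are never compared between arms. The documents do not support that. Protocol 14.3.8.1 tabulates events and subjects by arm, with severity and with causality to tralokinumab/placebo and to each vaccine, and it tests percentages of subjects with AEs and with related AEs. SAP 6.8.1 refers to AE tables by SOC as well as by preferred term, so SOC totals may also be shown. What is missing is the comparison at the level of the risk. Nor is the injection-site search the only grouping of AEs, because Panel 12 supplies six.

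Severe infections are also better served than the other two risks. Two AESI categories cover skin infection, serious cases fall under the SAE evaluation, and severity is shown by arm for each type of AE. The remaining gap is a single count of subjects with a severe infection at any site.

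Three further points count against the concern:

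- The list in Protocol 5.6 is introduced as examples and refers to the Investigator's Brochure, so the choice of injection site reactions may have grounds that are not visible here. This explains the search that was added. It does not supply the ones that are absent.
- Anaphylactic reactions and opportunistic infections are reasons for permanent discontinuation of IMP (Protocol 10.2.1), and reasons for discontinuation are shown by arm. However, AE is one broad category on the end-of-treatment form, so the specific risk is not visible there.
- The additional secondary safety endpoints are the number of AEs and the presence of ADA, and the plan delivers both. AE tests lie outside the testing hierarchy. This stands: no primary or secondary conclusion is affected.

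The even five-way split is close to a worst case, as step 4 of the working shows.

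**Conclusion.** The gap is real but limited. The plan pre-specifies no grouped term set and no by-arm subject count for hypersensitivity (including anaphylaxis) or immune complex disease, and only partial grouping for severe infections. A moderate excess spread over several terms could go unnoticed: at 10% v 2%, power falls from about 59% for one grouped count to between about 1% and 36% for a single line, depending on how far events concentrate.

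These figures rest on assumed rates, about 100 subjects per arm and assumed patterns of coding. They show the mechanism and do not forecast events. For very rare risks the gain is a clear, pre-specified count, not power. This is an inexpensive improvement to the description of safety. It does not correct an error in any planned test.

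**What to change.** In SAP 6.8.1, Other adverse events, add the following before unblinding:

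- (a) A MedDRA term set for hypersensitivity including anaphylaxis, searched on primary and secondary terms as is already done for injection site reactions.
- (b) A term set for immune complex disease, searched in the same way.
- (c) Severe infections, defined as events in the infections SOC recorded as serious or severe. Use these recorded attributes rather than opportunistic nature or parenteral treatment, because Protocol 13.3 describes neither a field for the former nor a link from an AE to a particular medication.

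For each group, report the number and percentage of subjects with at least one event by arm in the safety analysis set, with the risk difference and 95% CI. List (a) and (b) with ADA status, since the association of ADA with AEs is at present only optional (Protocol 14.3.8.5). State that the results are descriptive and outside the testing hierarchy.

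Cost: SAP wording, three tables from data already collected, and medical review of the term lists before unblinding. No new visits, samples or eCRF fields are needed, and no clinical rule changes.

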6.8.2 Vital signs

Vital signs will be summarised and listed.

For the summary tables of vital signs by visit, the last pre-dose vital sign assessment will be presented. If no dosing occurs at a visit, the last assessment recorded at the visit will be presented.

Potentially clinically significant values will be defined as displayed in Table 3.

Table 3: Potentially clinically significant vital signs values

Protocol parameter	SI unit	PCS low	PCS high
Systolic blood pressure	mmHg	<90 and decrease from baseline ≥ 20	≥ 180 and increase from baseline ≥ 20
Diastolic blood pressure	mmHg	<50 and decrease from baseline ≥ 15	≥ 105 and increase from baseline ≥ 15
Pulse	beats/min	<50 and decrease from baseline ≥ 15	≥ 120 and increase from baseline ≥ 15

Abbreviations: PCS=potentially clinically significant.

6.8.3 Electrocardiogram

ECG data will be summarised and listed. The overall central evaluation of ECG will be presented using shift tables.

6.8.4 Laboratory data

Laboratory data will be summarised and listed.

For the laboratory values, if the value is below the lower limit of quantification, half of the lower limit will be used for quantitative summaries. If the value is above the upper limit of quantification, the upper limit value will be used.

If more than laboratory value is reported for the same visit, the latest value will be used in summary statistics and analyses.

Potentially clinically significant values will be defined as displayed in [Table 4](#).

Table 4: Potentially clinically significant biochemistry and haematology values

Protocol lab parameter	SI unit	PCS low	PCS high
Biochemistry			
Sodium	mmol/L	< 129 mmol/L, < 125 mmol/L	> 160 mmol/L
Potassium	mmol/L	< 3 mmol/L, < 2.5 mmol/L	> 6.5 mmol/L, > 7.5 mmol/L
Creatinine	umol/L	N/A	> 1.5xULN, > 3xULN
Calcium	mmol/L	< 1.9 mmol/L	> 3.0 mmol/L, > 3.5 mmol/L
Alkaline phosphatase	U/L	N/A	> 3xULN
Aspartate aminotransferase	U/L	N/A	> 3xULN, > 5xULN, > 10xULN, > 20xULN
Alanine aminotransferase	U/L	N/A	> 3xULN, > 5xULN, > 10xULN, > 20xULN
Bilirubin	umol/L	N/A	> 2xULN
Cholesterol	mmol/L	N/A	> 6.2 mmol/L
LDL cholesterol	mmol/L	N/A	> 4.1 mmol/L, > 4.9 mmol/L
HDL cholesterol	mmol/L	N/A	> 1.6 mmol/L
Triglycerides	mmol/L	N/A	> 2.3 mmol/L, > 5.6 mmol/L
Glucose (non-fasting)	mmol/L	< 3.9 mmol/L	>11.1 mmol/L
Haematology			
Haemoglobin	g/L	<110 g/L, < 80 g/L	> 185 g/L for male, > 165 g/L for female
Neutrophils, absolute count	10 ⁹ /L	< 1.5×10 ⁹ /L, < 1.0×10 ⁹ /L, < 0.5×10 ⁹ /L	N/A
Lymphocytes, absolute count	10 ⁹ /L	< 1.0×10 ⁹ /L, < 0.5×10 ⁹ /L	> 5.0×10 ⁹ /L
Monocytes, absolute count	10 ⁹ /L	< 0.1×10 ⁹ /L	> 0.8×10 ⁹ /L
Eosinophils, absolute count	10 ⁹ /L	N/A	> 1.5, > 5.0
Basophils, absolute count	10 ⁹ /L	N/A	> 0.2
Thrombocytes	10 ⁹ /L	< 100×10 ⁹ /L, < 30×10 ⁹ /L, < 10×10 ⁹ /L	> 450×10 ⁹ /L

Abbreviations: HDL = high density lipoprotein; LDL = low density lipoprotein; N/A = not applicable; PCS = potentially clinically significant; ULN = upper limit of normal (i.e., upper limit of normal reference range).

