#### **14.3.8.3 Clinical laboratory evaluation**

The change in each of the laboratory parameters from baseline to each visit will be summarised by visit and treatment group as mean, standard deviation, median, minimum and maximum values for the safety analysis set.

Laboratory parameters will be classified as 'low', 'normal' or 'high', depending on whether the value is below, within or above the reference range, respectively. A shift table will be produced showing the categories at baseline against those at end of treatment. Subjects with laboratory parameters outside the reference range will be listed.

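### SAP Table 4 flags HDL cholesterol as potentially clinically significant only when it is high, although low is the unfavourable side; the error is confined to that one flag

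*SAP*

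**What the plan says.** SAP Section 6.8.4 makes Table 4 the definition of the PCS flag for biochemistry and haematology: "Potentially clinically significant values will be defined as displayed in" that table. The HDL row reads "HDL cholesterol mmol/L N/A > 1.6 mmol/L". In column order, that is the parameter, the unit, the low-side criterion and the high-side criterion. The table's footnote explains the entry on the low side: "N/A = not applicable; PCS = potentially clinically significant".

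The other three lipid rows have the same shape:
- "Cholesterol mmol/L N/A > 6.2 mmol/L"
- "LDL cholesterol mmol/L N/A > 4.1 mmol/L, > 4.9 mmol/L"
- "Triglycerides mmol/L N/A > 2.3 mmol/L, > 5.6 mmol/L"

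Protocol Section 14.3.8.3 handles laboratory values separately from this flag. Each parameter is classed as low, normal or high, "depending on whether the value is below, within or above the reference range, respectively". The section adds: "A shift table will be produced showing the categories at baseline against those at end of treatment". It also plans summaries of change from baseline at each visit by treatment group, and a listing of subjects with out-of-range values. SAP Section 4 keeps the protocol's analyses in force and presents the SAP as a supplement to them.

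**The concern.** A PCS flag should mark values that might matter clinically. For total cholesterol, LDL cholesterol and triglycerides, a high-only flag does that. For HDL the direction is reversed: a low value is unfavourable and a high one is generally favourable. The HDL row therefore appears to have the right form for a lipid but the wrong side for this one.

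What is at stake is the meaning of one line of safety output. A reader of the clinical trial report who sees HDL counts under a PCS heading would take them as possible harm, when they count subjects with favourable values. The same reader could take a low count as reassurance about HDL, when the flag cannot respond to a low value at all.

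**Working it through.** The documents state no figure to reproduce, and no sample size, power or error rate is involved. The check is a row-by-row reading of Table 4, set beside the protocol's other laboratory outputs.

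**1. What the HDL row does.** Low-side criterion: N/A, defined as not applicable. High-side criterion: above 1.6 mmol/L. A value at or below 1.6 mmol/L is never flagged, however low it is. A value above 1.6 mmol/L is always flagged.

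**2. Whether the table chooses sides deliberately.** Table 4 has 13 biochemistry rows and 7 haematology rows, 20 in all. They sort as follows:

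| Layout | Rows | Count |
|---|---|---|
| Two-sided | sodium, potassium, calcium, glucose, haemoglobin, lymphocytes, monocytes, thrombocytes | 8 |
| Low only | neutrophils | 1 |
| High only | creatinine, alkaline phosphatase, AST, ALT, bilirubin, total cholesterol, LDL, HDL, triglycerides, eosinophils, basophils | 11 |

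8 + 1 + 11 = 20. The layout varies by parameter, so N/A marks a side that is not to be flagged; it is not a default. HDL is one of four lipid rows, all high-only. That is consistent with the pattern of the other three having been carried over to HDL, but neither document says how the limits were chosen.

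**3. Whether either document gives a reason for a high-side HDL flag.** None was found. Neither document discusses HDL, gives a reference range for it, or explains the 1.6 mmol/L limit.

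**4. How often the flag is applied.** HDL belongs to the chemistry panel (Protocol Panel 11). Panel 2 schedules chemistry at screening and at Weeks 0, 4, 8, 12, 16 and 30. Subjects who transfer to the extension trial need not have the Week 30 visit (Protocol Section 7.1). The number of values above 1.6 mmol/L cannot be derived from the documents.

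**5. Where a low HDL value would still be seen.**

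| Output | Does it respond to low HDL? |
|---|---|
| PCS flag, SAP Table 4 | No |
| Change from baseline by visit and arm, with mean, SD, median, minimum and maximum (Protocol 14.3.8.3) | Yes; the minimum shows the largest individual fall at each visit |
| Low/normal/high shift table (Protocol 14.3.8.3) | Yes, for baseline against end of treatment |
| Listing of out-of-range values (Protocol 14.3.8.3) | Yes, with no restriction to two time points |
| Investigator evaluation of out-of-range results, with repeat testing from baseline on if clinically significant, and AE reporting after the first screening visit (Protocol 11.4.5) | Yes |

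The shift table, listing and investigator evaluation depend on the central laboratory having a lower reference limit for HDL. The change summaries do not.

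**The case against.** The strongest objection is that the documents never say low HDL is the unfavourable side, so the row contradicts nothing in them. That is correct as far as it goes. A reader might infer an internal contradiction, and there is none to cite. The premise is, however, the ordinary reading of a routine laboratory test and does not depend on any particular outside study or figure. A sponsor wishing to keep a high-side flag would also have to explain why the low side is not applicable.

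The second objection is that the consequence is easily overstated. This stands, and it rules out several stronger readings:

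- A reader might infer that the trial cannot show a fall in HDL. Protocol Section 14.3.8.3 and the investigator review in Section 11.4.5 do not support that. Only the PCS flag is blind to a fall.
- A reader might treat the PCS table as the only screen of individual laboratory values. The SAP does not say so, and the out-of-range listing and investigator review also work at the level of the individual.
- A reader might count the lack of a change-from-baseline condition as part of the HDL fault. The vital-sign limits in SAP Table 3 have such a condition, but no row of Table 4 does, so it says nothing about HDL in particular.
- A reader might assume HDL is measured at every scheduled time in every subject. Transfer to the extension trial removes Week 30 for some.

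A third objection concerns the remedy. A low-side limit set at the bare lower reference limit would repeat the low category and the listing that the protocol already provides. The limits in Table 4 that are tied to the reference range are multiples of its upper limit, from 1.5 to 20 times. This stands too, so no cut-off is proposed here.

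**Conclusion.** The point holds as a minor error in a safety-output definition. As written, the HDL row flags values on the favourable side and cannot flag values on the unfavourable side. The fault lies in 1 of 20 rows of Table 4 and in the PCS output alone. It does not affect the primary vaccine-response endpoints, the secondary efficacy endpoints or the other laboratory outputs.

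The conclusion rests on one assumption from outside the documents, namely that low HDL is the unfavourable direction. The view that its effect is small also assumes that the central laboratory reports a lower reference limit for HDL, so that the shift table and listing work as intended; even without one, the by-visit change summaries would remain. The number of subjects who would be flagged is unknown. That the layout was copied from the other lipid rows is plausible but not shown.

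**What to change.** Before the PCS tables are produced, change the HDL row of SAP Table 4 so that the high side reads N/A, and take one of two routes for the low side:

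1. Enter a low-side limit chosen by the sponsor's medical expert, with a short written justification, because the documents supply no figure.
2. Leave both sides N/A and state that low HDL is covered by the change summaries, shift table and out-of-range listing of Protocol Section 14.3.8.3.

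Either route removes the misdirected flag. The first also gives an HDL flag on the unfavourable side; the second gives no HDL flag at all. The cost is one table row, the matching program line and a note of the change in the SAP or the clinical trial report. No new data are needed.
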